1 SYNOPSIS

Not applicable.

2 SCHEDULE OF ACTIVITIES

Study assessments and procedures are presented in Table 2-1 and [Table 2-2](#).

Table 2-1: Screening Procedural Outline (CV185687)

| Procedure | Screening Visit (Day -28 to Day -2) | Admission Visit (Day -1) | Notes |
|--------------------------------|--|-----------------------------|--|
| Eligibility Assessments | | | |
| Informed Consent | X | | A participant is considered enrolled only when a protocol-specific informed consent is signed. |
| Inclusion/Exclusion Criteria | X | X | |
| Medical History | X | X | A complete medical history will be obtained during screening. Interim medical history on Day -1. Include any toxicities or allergy related to previous treatments. |
| Report to Study Site | | X | |
| Safety Assessments | | | |
| Physical Examination | X | X | The physical examination performed on Day -1 should be done within 24 hours of dosing on Day 1. Starting on Day -1, standard baseline medical dermatology photographs of areas affected by rash will be taken. If there are any changes with the affected areas or new areas of rash are detected, additional photographs will be obtained. |
| Physical Measurements | X | X | Height and weight at screening; weight only on Day -1. Body mass index will be calculated at screening and on Day -1. |
| Vital Signs | X | X | Includes body temperature, respiratory rate, and sitting blood pressure and heart rate. Blood pressure and heart rate should be measured after the participant has been sitting for at least 5 minutes. |
| 12-Lead ECGs | X | X | 12-lead ECGs should be recorded after the participant has been supine for at least 5 minutes. |
| Clinical Laboratory Tests | X | X | Includes blood and urine samples. Full clinical laboratory tests will be done including coagulation parameters (aPTT, INR, and PT) will be measured. Participants are required to fast for at least 8 hours prior to |

Table 2-1: Screening Procedural Outline (CV185687)

| Procedure | Screening Visit (Day -28 to Day -2) | Admission Visit (Day -1) | Notes |
|--------------------------------|--|-----------------------------|--|
| | | | the collection of specimens for clinical laboratory tests. Results of screening clinical laboratory tests must be available prior to admission to the clinic on Day -1. Results of clinical laboratory tests performed on Day -1 must be available prior to dosing on Day 1. See Section 9.4.4 . |
| Serology | X | | Results must be reviewed prior to admission to the clinic on Day -1. See Section 9.4.4. |
| Urine Drug Test | X | X | Includes alcohol and cotinine. Results of screening urine drug tests must be available prior to admission to the clinic on Day -1. Results of urine drug tests performed on Day -1 must be within 24 hours and reviewed prior to dosing on Day 1. See Section 9.4.4. |
| Pregnancy Test (serum) | X | X | All women. Results of pregnancy tests must be available prior to admission to the clinic on Day -1. The pregnancy test on Day -1 must be within approximately 24 hours, and results must be available prior to dosing on Day 1. Serum pregnancy tests must be reported in a quantitative result. |
| Follicle Stimulating Hormone | X | | Postmenopausal women only. Refer to Appendix 4 . |
| Adverse Event Reporting | | | |
| Monitor for SAEs | X | X | All SAEs must be collected from the date of participant's written consent until 30 days post discontinuation of dosing or participant's participation in the study if the last scheduled visit occurs at a later time. |

aPTT = activated partial thromboplastin time; ECG = electrocardiogram; INR = international normalized ratio; PT = prothrombin time; SAE = serious adverse event

Table 2-2: On Treatment Procedural Outline (CV185687)

| Procedure | D1 | D2 | D3 | D4 | D5 | D6 | D7 | D8 (Study Discharge) ^a | Notes |
|---------------------------|----|----|----|----|----|----|----|--------------------------------------|--|
| Safety Assessments | | | | | | | | | |
| Physical Examination | | | | X | | | | X | Day 4 physical examination targeted for skin will be performed within 24 hours of dosing on Day 5. Starting on Day -1, standard baseline medical dermatology photographs of areas affected by rash will be taken. If there are any changes with the affected areas or new areas of rash are detected, additional photographs will be obtained. |
| Physical Measurements | | | | | | | | X | Weight only. |
| Vital Signs | X | | | | X | | | X | Vital signs will be obtained prior to dosing on Days 1 and 5. See note in screening procedures. |
| 12-Lead ECGs | | | | | X | | | X | 12-lead ECGs on Day 5 will be obtained prior to dosing. See note in screening procedures. |
| Clinical Laboratory Tests | | | | X | | | X | | Includes blood and urine samples. Full clinical laboratory tests will be done including coagulation parameters (aPTT, INR, and PT) will be measured on Days 4 and 7. Results of clinical laboratory tests performed on Day 4 must be available prior to dosing on Day 5. See note in screening procedures and Section 9.4.4 . |
| Pregnancy Test (serum) | | | | X | | | X | | Serum pregnancy testing must be done within approximately 24 hours of Day 5. Results must be reviewed prior to dosing on Day 5. Serum pregnancy tests must be reported in a quantitative result. |

Table 2-2: On Treatment Procedural Outline (CV185687)

| Procedure | D1 | D2 | D3 | D4 | D5 | D6 | D7 | D8 (Study Discharge) ^a | Notes |
|--------------------------------|----|----|----|----|----|----|----|--------------------------------------|---|
| Adverse Event Reporting | | | | | | | | | |
| Monitor for Nonserious AEs | X | X | X | X | X | X | X | X | Nonserious AEs will be collected from the initiation of study treatment (Day 1) until 3 days after the last dose of study treatment. |
| Monitor for SAEs | X | X | X | X | X | X | X | X | See note in screening procedures. |
| PK Assessments | | | | | | | | | See Table 9.5-1 . An additional PK sample may be collected in the event of discontinuation due to an AE. |
| Serial Blood PK Sampling | X | X | X | X | X | X | X | X | See Section 9.5 . |
| Clinical Drug Supplies | | | | | | | | | |
| Randomize | X | | | | | | | | Randomization will occur prior to study drug administration. |
| Apixaban Administration | X | | | | X | | | | See Section 7 . |
| Other Assessments | | | | | | | | | |
| Palatability Assessment | X | | | | X | | | | For both treatments. Palatability assessment will be completed immediately (within 5 minutes) after administration of the apixaban 0.5-mg tablet and 0.1-mg sprinkle capsule dosages. Refer to Appendix 6 . |

^a Evaluations performed prior to study discharge or for participants who are prematurely discontinued.

AE = adverse event; aPTT = activated partial thromboplastin time; D = Day; ECG = electrocardiogram; INR = international normalized ratio; PK = pharmacokinetic; PT = prothrombin time; SAE = serious adverse event

In the event multiple procedures are required at a single time point, the 12-lead electrocardiogram (ECG) may be obtained up to 15 minutes earlier, vital signs may be obtained up to 10 minutes earlier or later, and the clinical laboratory blood sample may be obtained up to 5 minutes earlier than the nominal time point, ensuring the pharmacokinetic (PK) samples can be collected on time. For predose procedures, vital signs within 30 minutes of dose, 12-lead ECG within 45 minutes, and predose PK collected within 15 minutes of dose. Vital signs and 12-lead ECG measurements should be performed before clinical laboratory and PK blood samples are collected.

3 INTRODUCTION

Factor Xa (FXa) plays a pivotal role in the coagulation cascade at the junction of the intrinsic and extrinsic pathways of the coagulation system. Inhibition of FXa is expected to exert anticoagulant and antithrombotic effects by decreasing the conversion of prothrombin to active thrombin, thereby diminishing thrombin-mediated activation of the coagulation process, including fibrin formation and platelet activation. Apixaban is an orally active, selective, reversible inhibitor of FXa and is approved for prevention of venous thromboembolism in patients who have undergone elective knee or hip replacement surgery, for stroke prevention in nonvalvular atrial fibrillation, and for treatment of venous thromboembolism and prevention of recurrent venous thromboembolism [USPI¹ and SmPC²].

[REDACTED]

3.3 Benefit/Risk Assessment

Since this is not an efficacy treatment study, there is no direct benefit to the participants participating in this study other than contributing to the research of a product.

The potential risk to participants from apixaban in this study is expected to be minimal. Approved apixaban doses are 2.5 mg twice daily (BID) in venous thromboembolism prevention in orthopedic patients, 5 mg BID in atrial fibrillation, and 10 mg BID for 7 days followed by 5 mg BID in venous thromboembolism treatment. In healthy participants, single and multiple oral doses of apixaban up to 25 mg BID for 7 days and 50 mg once daily for 3 days were well-tolerated. In this study, single 2.5-mg doses of apixaban will be administered under medical supervision; each single dose will be separated by a washout period of at least 4 days. To ensure safety, participants with potential risk factors for bleeding will be excluded; this includes any history or evidence of abnormal bleeding or coagulation disorders, intracranial hemorrhage, or abnormal bleeding or coagulation disorders in a first degree relative.

Apixaban did not directly impair fertility or early embryonic development in rats and was not teratogenic in mice, rats, or rabbits at area under the concentration-time curve (AUC) multiples $\leq 6.9 \times$ the human AUC at 20 mg (10 mg BID). However, the reproductive risk of apixaban has not been evaluated in humans. Therefore, women of childbearing potential (WOCBP) who are unwilling or unable to use an acceptable method of contraception ([Appendix 4](#)) to avoid pregnancy for at least 4 weeks prior to dosing, during the study, and 33 days after the last dose of study treatment in such a manner that the risk of pregnancy is minimized will be excluded. In addition, male participants must agree to use an acceptable method of contraception during the entire study and for 93 days after the last dose. Male participants must not donate sperm during the entire study and for 93 days after the last dose.

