5.3 End of Study Definition

The start of the trial is defined as first visit for the first participant screened. End of trial is defined as the date of the last health status follow-up contact made to a participant discharged from the study. Study completion is defined as the final date on which data for the primary endpoint was or is expected to be collected, if this is not the same.

The approximate duration of this study will be 36 days, including a 28-day screening period.

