6.1 Inclusion Criteria

1) Signed Written Informed Consent

- a) The signed informed consent form.

2) Type of Participant and Target Disease Characteristics

- a) Healthy participants as determined by no clinically significant deviation from normal in medical history, physical examination, 12-lead ECGs, vital signs, and clinical laboratory tests including coagulation parameters.
- b) Body mass index (BMI) of 18.0 to 30.0 kg/m², inclusive. Body mass index = weight (kg)/[height(m)]².
- c) Participant Re-enrollment: This study permits the re-enrollment of a participant who has discontinued the study as a pretreatment failure (ie, has not been treated). If re-enrolled, the participant must be re-consented if outside of screening window (along with verification of eligibility).

3) Age and Reproductive Status

- a) Males and Females, ages 18 to 45 years, inclusive.
- b) Women of childbearing potential must have a negative quantitative serum pregnancy test (minimum sensitivity 25 IU/L or equivalent units of human chorionic gonadotropin) within approximately 24 hours prior to the start of study treatment. Serum pregnancy tests will be performed at screening and Day -1.
- c) Women must not be breastfeeding.
- d) Women of childbearing potential must agree to follow instructions for method(s) of contraception for the duration of treatment with study treatment apixaban plus 5 half-lives of study treatment apixaban (~3 days) plus 30 days (duration of ovulatory cycle) for a total of 33 days post-treatment completion ([Appendix 4](#)).
- e) Males who are sexually active with WOCBP must agree to follow instructions for method(s) of contraception ([Appendix 4](#)) for the duration of treatment with study treatment apixaban plus 5 half-lives of study treatment apixaban (~3 days) plus 90 days (duration of sperm turnover) for a total of 93 days post-treatment completion. In addition, male participants must be willing to refrain from sperm donation during this time.

- f) Azoospermic males are exempt from contraceptive requirements. Women of childbearing potential who are continuously not heterosexually active are also exempt from contraceptive requirements, and still must undergo pregnancy testing as described in this section.

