APPENDIX 4 WOMEN OF CHILDBEARING POTENTIAL DEFINITIONS AND METHODS OF CONTRACEPTION

DEFINITIONS

Woman of Childbearing Potential (WOCBP)

A woman is considered fertile following menarche and until becoming post-menopausal unless permanently sterile. Permanent sterilization methods include hysterectomy, bilateral salpingectomy, and bilateral oophorectomy.

Women in the following categories are not considered WOCBP

- Premenarchal
- Premenopausal female with 1 of the following:
 - Documented hysterectomy
 - Documented bilateral salpingectomy
 - Documented bilateral oophorectomy

Note: Documentation can come from the site personnel's review of the participant's medical records, medical examination, or medical history interview.

- Postmenopausal female
 - A postmenopausal state is defined as 12 months of amenorrhea in a woman over age 45 years in the absence of other biological or physiological causes. In addition, females under the age of 55 years must have a serum follicle stimulating hormone, (FSH) level > 40 mIU/mL to confirm menopause.

Note: Females treated with hormone replacement therapy, (HRT) are likely to have artificially suppressed FSH levels and may require a washout period in order to obtain a physiologic FSH level. The duration of the washout period is a function of the type of HRT used. The duration of the washout period below are suggested guidelines and the investigators should use their judgement in checking serum FSH levels.

- 1 week minimum for vaginal hormonal products (rings, creams, gels)
- 4 week minimum for transdermal products
- 8 week minimum for oral products

Other parenteral products may require washout periods as long as 6 months. If the serum FSH level is > 40 mIU/ml at any time during the washout period, the woman can be considered postmenopausal.

CONTRACEPTION GUIDANCE FOR FEMALE PARTICIPANTS OF CHILDBEARING POTENTIAL

One of the highly effective methods of contraception listed below is required during study duration and until the end of relevant systemic exposure, defined as 5 weeks (33 days) after the end of study treatment, plus 30 days.

Local laws and regulations may require use of alternative and/or additional contraception methods.

| |
|---|
| 
Highly Effective Contraceptive Methods That Are User Dependent
 
Failure rate of <1% per year when used consistently and correctly.^a
 |

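### The 4-week pre-dose contraception requirement in Protocol Section 3.3 is not carried into any visible eligibility criterion

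*Protocol*

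**What the plan says.** Four parts of the protocol bear on when contraception must start.

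- **Section 3.3 (Benefit/Risk Assessment).** Because reproductive risk has not been evaluated in humans, WOCBP unwilling or unable to use an acceptable method "to avoid pregnancy for at least 4 weeks prior to dosing", then during the study and for 33 days after the last dose, are to be excluded.
- **Section 6.1, inclusion 3d.** WOCBP "must agree to follow instructions for method(s) of contraception for the duration of treatment with study treatment apixaban plus 5 half-lives" (about 3 days) and a further 30 days, a total of 33 days after treatment. No period before dosing is mentioned.
- **Section 6.1, inclusion 3f.** "Women of childbearing potential who are continuously not heterosexually active are also exempt from contraceptive requirements", although they are still tested for pregnancy.
- **Appendix 4, guidance for women.** A highly effective method "is required during study duration and until the end of relevant systemic exposure". The start of the study duration is not defined there. Section 5.3 says: "The approximate duration of this study will be 36 days, including a 28-day screening period".

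On testing, inclusion 3b asks for a negative serum result within about 24 hours before treatment and adds: "Serum pregnancy tests will be performed at screening and Day -1". Table 2-2 adds tests on Days 4 and 7. For the Day 4 test it says: "Results must be reviewed prior to dosing on Day 5".

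Section 6 makes its criteria mandatory before the Day 1 dose and grants no exceptions. The visible text of Sections 6.2 and 6.3 does not mention contraception.

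**The concern.** Section 3.3 gives a safety exclusion with a stated reason, but the list that sites use to admit participants does not contain it. The other time limits in the same paragraph of Section 3.3 do reach Section 6: 33 days for women (3d), and 93 days for men with no sperm donation (3e). Only the 4-week lead-in is missing, which looks like an omission rather than a decision.

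A heterosexually active WOCBP who starts contraception at a late screening visit, and tests negative at screening and on Day -1, meets every visible criterion in Section 6. She can be dosed on Day 1 although Section 3.3 says she is excluded. An ethics committee that relies on Section 3.3 would believe in a safeguard that the entry criteria do not apply.

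**Working it through.** **Inputs**

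- Required lead-in: at least 4 weeks = 4 × 7 = 28 days (Section 3.3).
- Screening window, from the column heading in Table 2-1: "Screening Visit (Day -28 to Day -2".
- Confinement from Day -1 to discharge on Day 8 (Section 5.1).
- Study duration of 36 days, including 28 days of screening (Section 5.3).

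**The plan's own figures**

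- 28 screening days + 8 days (Days 1 to 8) = 36 days, which agrees with Section 5.3. The protocol's stated duration therefore includes screening.
- 3 + 30 = 33 days after treatment in 3d, which agrees with Section 3.3. The two sections differ only in the period before dosing.

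**Lead-in under each text**

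There is no Day 0, so Day -k is k days before the Day 1 dose. The shortfall is 28 - k.

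| Text | Contraception starts | Days before dose | Shortfall from 28 |
|---|---|---|---|
| Section 3.3 | 4 weeks or more before dosing | at least 28 | 0 |
| Inclusion 3d | with treatment | 0 | 28 |
| Appendix 4, duration counted from screening | Day -28 to Day -2 | 28 to 2 | 0 to 26 |
| Appendix 4, duration counted from admission | Day -1 | 1 | 27 |

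**Permitted screening days that fall short**

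For a woman who starts contraception at her screening visit:

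- Permitted days: k = 2 to 28, so 28 - 2 + 1 = 27 days.
- Days with k < 28: k = 2 to 27, so 26 of 27, with a shortfall of 1 day (k = 27) to 26 days (k = 2).
- Only a screening visit on Day -28 gives the full 28 days.

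This is a count of calendar days, not of women.

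**Whether another provision supplies the lead-in**

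- The tests at screening and on Day -1 show pregnancy status on those days. They do not require prior contraception, and a serum test on Day -1 cannot rule out a conception too recent to detect.
- The Day 4 test protects the Day 5 dose only; the Day 1 dose has already been given.
- Confinement starts on Day -1 and cannot cover the preceding weeks.
- Exclusion 1s leaves other reasons to the investigator's judgement and sets no 4-week rule.
- Exclusion 5c refers to Section 6.3, which covers diet, caffeine, alcohol, tobacco and activity.
- Exclusion 2a refers to Section 7.7.1, which is redacted and cannot be checked.

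**The case against.** The strongest objections are these.

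- **Redaction.** Section 7.7.1 is imported by exclusion 2a and might contain the lead-in. This stands as a limit, so the finding concerns the visible criteria only. Even if 7.7.1 stated the lead-in, 3d and Appendix 4 would still give different starting points.
- **Section 3.3 is itself protocol text.** The study must comply with the whole protocol, and neither 3d nor Appendix 4 forbids starting earlier. A site could satisfy all three by applying the longest period. That is true, but Section 6 is the mandatory entry list, and a site that works from it would not know to apply the longer period.
- **Size.** The count of 26 of 27 days assumes that contraception starts exactly at screening and that the study duration begins there. The number of women affected could be zero among about 30 participants of both sexes. This is correct. Women who have already used a method for 4 weeks, and those exempt under 3f, are not affected.
- **Consequence.** Exposure is two single 2.5-mg doses under confinement, with repeated serum tests. Section 3.3 reports no teratogenicity in three animal species. No endpoint, sample size or analysis changes. This also stands. It limits the importance of the point without removing the mismatch.
- **Neighbouring text.** The same Appendix 4 sentence describes 33 days as 5 weeks (5 × 7 = 35) and then adds 30 days (33 + 30 = 63), against 33 in total in Sections 3.3 and 6.1. Section 3.3 asks for an acceptable method, while Appendix 4 asks for a highly effective one. These are separate mismatches, but whoever edits the sentence should settle them too.

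**Conclusion.** The point holds. Section 3.3 requires at least 28 days of contraception before dosing. Inclusion 3d requires none. Appendix 4, read with Section 5.3, gives 2 to 28 days to a woman who starts at screening, which is 1 to 26 days short on 26 of the 27 permitted screening days.

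The Appendix 4 figures assume that the study duration starts at the screening visit. A later start would widen the gap. The finding covers visible text only, because Section 7.7 is redacted. It concerns heterosexually active WOCBP who have not already used a method for 4 weeks, and their number is not in the documents.

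This is an inconsistency between a stated safety exclusion and the operative criteria. It decides who may be dosed, so it should be corrected. The clinical risk is small, and the bioavailability comparison is not affected.

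**What to change.** Add a requirement for contraception for at least 4 weeks before dosing to inclusion 3d and to the Appendix 4 guidance for women, and keep the 3f exemption. Confirm it by contraceptive history at screening and on Day -1, when Table 2-1 already schedules medical history. The screening window need not change, because prior use can be taken by history.

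The cost is one line in each place and possibly a few deferred women. A woman who starts contraception at a Day -2 screening would be deferred by 26 days. Her dose would then fall 2 + 26 = 28 days after screening, still within the 28-day limit. A woman who starts after her screening visit would pass that limit and need rescreening, and the protocol already permits re-enrolment of participants who have not been treated.

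If the sponsor does not intend the lead-in, the alternative is a single correction to Section 3.3, so that the benefit/risk statement matches the criteria actually applied.

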4 OBJECTIVES AND ENDPOINTS

Table 4-1: Objectives and Endpoints

| Objectives | Endpoints |
|---|---|
| 
Primary
 
 To assess the bioavailability of apixaban 0.1-mg sprinkle capsules relative to apixaban 0.5-mg tablets, both administered orally in healthy participants | 
 Cmax, AUC(INF), AUC(0-T) |
| 
Secondary
 
 To assess the safety and tolerability of apixaban To assess the PK of apixaban 0.1-mg sprinkle capsules To assess the PK of apixaban 0.5-mg tablets | 
 Incidence of nonserious AEs, SAEs, and AEs leading to discontinuation; and results of vital signs, 12-lead ECGs, physical examinations, and clinical laboratory tests Tmax, T-HALF, Frel |
| 
██████████ ██████████ ██████████ 0.1-mg sprinkle capsules
 | 
██████████
 |

[figure not shown]
